#### **9.4.2 Secondary outcomes**

Secondary outcome measures will be biochemistry laboratory tests before and after multifaceted interventions.

### **9.4 Data Analyses**

We will calculate descriptive statistics for participants' baseline characteristics and primary and secondary outcomes. The bivariate analysis will be performed using the t-test or Mann-Whitney U test for continuous variables with normal or non-

normal distribution, respectively. Chi-squared test for categorical variables will be used to test correlations between baseline characteristics, change of laboratory results and outcomes. The paired t-test will be used to examine the difference between before and after the interventions. Stepwise multivariate logistic regression models will be used to identify the correlates of outcomes after adjusting for potential confounders. All tests conducted will be two-tailed, and significance will be set at  $p < 0.05$ .

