## 2 BACKGROUND AND RATIONALE

### 2.1 Background on Condition, Disease, or Other Primary Study Focus

Previous studies among CKD patients found the fracture incidence to progressively increase by 15.0, 20.5, 24.2, 31.2, and 46.3 per 1000 person-years for CKD stages 1 to 2, 3a, 3b, and 4, respectively. The risk of fracture increases to 5 times higher in patients with an estimated glomerular filtration rate (eGFR) <15 versus >60 ml/min per 1.73 m^2). Patients with CKD and older than 65 years of age have a higher rate of fractures during 3-years of follow-up. It would be an important issue to prevent skeletal fracture among older adults with CKD since fracture can cause higher mortality and health resource utilization and loss of quality of life.

Renal osteodystrophy is used previously to describe the histological changes of bone among CKD patients. However, these changes in mineral and bone metabolism were derived from dysregulation during renal function deterioration gradually. Therefore, the mineral and bone disorder associated with CKD is an evolving entity which caused abnormalities of mineral metabolism, bone turnover, and vascular calcification. The KDIGO CKD-MBD guideline suggests that a bone biopsy should be considered for patients with a presentation of bone pain or unexplained fracture. A transiliac bone biopsy after tetracycline labeling is the gold-standard technique for diagnosis of CKD-MBD. However, this invasive measure might not be acceptable to many patients and only few centers have the expert histomorphometry analyzers. In clinical practice, the primary osteoporosis is a more prevalent disease among older adults. The KDIGO CKD-MBD also suggested application of dual-energy x-ray absorptiometry (DXA) in evaluation the fracture risk among CKD patients. In order to prevent fragility fracture, it would be reasonable to target abnormalities of mineral metabolism and primary osteoporosis. Further studies for CKD-MBD would be considered for those with unexplained fractures or bone pain. Tools to evaluate osteoporosis and CKD-MBD are briefly described below.

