### **3 STUDY DESIGN**

The design is a pilot study with data collection through interviews, and medical records. There is one study arm: the intervention. A description of multi-faceted intervention on osteoporosis and CKD-MBD can be found in STUDY INTERVENTIONS. The pilot will take place at two primary clinical care practices in National Taiwan University Hospital and its Chu-Tung Branch in Taiwan. 60 patients will be enrolled and followed for up from January 1, 2020 to December 31, 2020 with interviews and medical record reviews. Participants will undergo a baseline and follow-up interview to collect patient reported baseline and outcome measures.

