## **6 STUDY PROCEDURES**

### **6.1 Schedule of Evaluation for Patient Population**

| Time period          | Screening | Informed Consent (Enrollment) | Clinic visit | Interviews (Patient Reported Outcomes) | Blood and Urine Examination | Bone density and Thoracolumbar x-ray film |
|----------------------|-----------|-------------------------------|--------------|--|-----------------------------|---|
| Enrollment (Day 1)   | x         | x                             | x            |  | x                           | x   |
| Follow-up Evaluation |           |                               | x            | x                                      | x                           |   |

|                                |  |  |  |  |  |  |
|--------------------------------|--|--|--|--|--|--|
| (3,6,9,12 th month) |  |  |  |  |  |  |
|--------------------------------|--|--|--|--|--|--|

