## **STATISTICAL CONSIDERATIONS**

### **9.1 Sample Size**

As this is a pilot study, we did not complete a formal sample size calculation. The chosen sample size is based upon the estimated number of patients that the funding supports their blood and urine examination, and bone density examination.

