### **9.2 Outcomes**

#### **9.2.1 Primary outcomes**

The primary outcome measures will be all-cause mortality, cardiovascular events, subsequent fracture rate, and fall rate from January 1, 2020 to December 31, 2020. The primary outcome measures will be collected during the baseline and follow-up (3-12 months) interviews in clinics.

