## 12 RESULTS

### 12.1 Number of Patients Screened

A total of 249 patients in outpatient clinic of two investigators were screened for osteoporosis risk assessment. If FRAX® screening criteria for Hip fracture risk: men with risk > 6%, women > 7% or major fracture risk: men > 15%, Women > 12.5% were reached. Those with exclusion criteria were excluded. Finally, from January 1, 2020 to December 31, 2020, 5 participants were enrolled for multifaceted interventions. After the intervention, 5 people had laboratory testing, bone density examination and health education during follow-up but no one completed the study. The study was terminated because of funding was only for one year. A total of 133 patients were screened in National Taiwan University Hospital, and a total of 116 patients were screened in Chu-Tung Branch, with an average age of 75.7 years. A total of 138 patients accounted for 55.4% of men. The average weight of men was 66.3kg, the average women were 57.3kg, and the average serum creatinine level 2.0 mg/dL for men and 1.8 mg/dL for women. The estimated glomerular filtration rate (eGFR) was 41.9ml/min/1.73m^2 for men and 38.1ml/min/1.73m^2 for women (Table 1). In the analysis of the reasons for exclusion, the highest was the lower risk of fractures estimated by FRAX® which accounted for 128 (51.4%), followed by failure to perform behavioral interventions (17.7%) and patients' refusal (15.7%).

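### Section 9.4 looks for correlates of outcomes by unrestricted stepwise logistic regression in at most 60 patients; about 1 to 3 expected fractures cannot support such a model, and a yes/no model does not model the named fall and fracture rates.

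*Combined protocol and SAP*

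**What the plan says.** Section 9.4 (Data Analyses) plans descriptive statistics for baseline characteristics and for the primary and secondary outcomes, then bivariate tests, a paired t-test, and this: "Stepwise multivariate logistic regression models will be used to identify the correlates of outcomes after adjusting for potential confounders". The chi-squared test is to be "used to test correlations between baseline characteristics, change of laboratory results and outcomes". All tests are two-sided at p<0.05. The section does not say which outcomes are modelled, which variables are candidates, which test or rule governs entry and removal, how many events are needed before a model is fitted, or that the analysis is exploratory.

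Section 9.2.1 names four primary outcomes. Besides all-cause mortality and cardiovascular events, they are "subsequent fracture rate, and fall rate from January 1, 2020 to December 31, 2020".

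Section 3 gives the size and period: "60 patients will be enrolled and followed for up from January 1, 2020 to December 31, 2020". Section 6.1 schedules follow-up at "3,6,9,12 th month". Section 9.1 states: "As this is a pilot study, we did not complete a formal sample size calculation". Section 4.1 restricts entry to CKD stage 3-4 with a raised FRAX risk. The only event rates in the documents are the fracture rates in Section 2.1: "15.0, 20.5, 24.2, 31.2, and 46.3 per 1000 person-years for CKD stages 1 to 2, 3a, 3b, and 4".

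**The concern.** Stepwise selection needs many events per candidate variable. Here the sample is small, one primary outcome is expected to be very rare, and the candidate set is open. Such a procedure tends either to fail, with separated or unstable estimates, or to return variables that entered by chance. Nothing in Section 9.4 would tell a reader of the resulting list that it is exploratory.

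There is also a mismatch of quantity. Two of the four primary outcomes are rates, but logistic regression models whether an event occurred. A patient with four falls counts the same as a patient with one, and a patient observed for three months counts the same as one observed for twelve.

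At stake is a published list of correlates that could contain chance findings, and a multivariable analysis that does not address the fall and fracture rates the plan names.

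**Working it through.** The plan states no power, event count or sample-size calculation, so there is no figure of its own to reproduce.

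**1. Expected fractures**

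Inputs: 60 patients (Section 3); at most one year each, so at most 60 person-years (Sections 3 and 9.2.1); rates from Section 2.1; stages 3-4 eligible (Section 4.1). Section 2.1 prints five rates for four stage groups, so the mapping is ambiguous. The first rate, 15.0, is listed against stages 1 to 2, which are not eligible. The other four are all kept.

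Expected fractures = rate × person-years / 1000, with Poisson probabilities:

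| Rate per 1000 | Expected in 60 person-years | P(none) | P(5 or more) |
|---|---|---|---|
| 20.5 | 1.23 | 29% | 0.9% |
| 24.2 | 1.45 | 23% | 1.6% |
| 31.2 | 1.87 | 15% | 4.2% |
| 46.3 | 2.78 | 6% | 15% |

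- If 24.2 is read as the stage 3a rate, the range is 1.5 to 2.8 instead of 1.2 to 2.8.
- If patients enter evenly over 2020 (assumption), there are about 30 person-years and 0.6 to 1.4 fractures.
- The Section 2.1 rates are by CKD stage, whereas Section 4.1 also selects on FRAX. If that doubled the rate (assumption), 41.0 × 60/1000 = 2.5 and 92.6 × 60/1000 = 5.6 fractures. At 5.6, P(5 or more) is 65%, but P(10 or more) is only about 6%.
- As an illustration of precision, 2 fractures in 60 person-years have an exact Poisson 95% CI of 4.0 to 120.4 per 1000, wider than the whole Section 2.1 range.

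**2. Entry of pure-noise variables**

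Assumptions: n = 60; 5, 10 or 15 independent candidates unrelated to the outcome; forward entry at p<0.05; samples with no event set aside. With independent tests, the chance that at least one is significant is 1 − 0.95^k: 23%, 40% and 54% for k = 5, 10 and 15.

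Simulated share of models that select at least one noise variable, likelihood-ratio entry, 2,000 models per cell:

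| Event risk | 5 candidates | 10 candidates | 15 candidates |
|---|---|---|---|
| 5% | 28.6% | 49.5% | 63.6% |
| 10% | 26.9% | 43.5% | 58.0% |
| 30% | 24.7% | 41.2% | 57.0% |

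Across repeat runs at event risks of 5 to 30%, the range is about 22 to 64% with likelihood-ratio entry and 12 to 50% with Wald entry. At 2% risk, Wald entry gives only about 6 to 13%, because the estimates are unstable. Section 9.4 names no test, so all of these are possible. Most of the effect is ordinary multiplicity, as comparison with 1 − 0.95^k shows.

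**3. What a yes/no model of falls loses**

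The documents give no fall rate; 0.3 to 1.0 falls per person-year is assumed. Over a full year with Poisson falls at rate λ, the share of falls dropped is 1 − (1 − e^−λ)/λ:

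- λ = 0.3: 1 − 0.259/0.3 = 14%
- λ = 0.6: 1 − 0.451/0.6 = 25%
- λ = 1.0: 1 − 0.632/1.0 = 37%

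If falls cluster in some patients (negative binomial, dispersion 1), the share is 1 − 1/(1 + λ), or 23 to 50% over the same rates.

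**4. Time observed**

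Sections 3 and 9.2.1 place enrolment and follow-up inside calendar 2020. Section 6.1 schedules a month-12 visit. Both hold only if everyone enrols at the start of January. Otherwise observation time differs between patients, and the logistic model takes no account of it.

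**The case against.** The study is a single-arm pilot with a sample size set by funding, and Section 9.1 says so. That explains the small number, but it places no limit on the model that Section 9.4 commits to.

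Several stronger readings are tempting, and the documents do not support them:

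- *That the fall and fracture rates are not estimated at all.* Section 9.4 opens with descriptive statistics for the primary outcomes, so some reporting of them is planned. What stands is narrower: no person-time denominator, confidence interval or repeat-fall method is specified, and the only multivariable model is yes/no.
- *That no outcome can be modelled.* The event shortage is shown for fractures alone. At the assumed fall rates, 10 or more of 60 patients would fall with probability 91 to 100% over a full year, enough for one covariate by a common rule of thumb.
- *That noise is often selected whatever the software does.* With Wald entry at fracture-level risk it is not; there the model fails through instability.
- *That unequal observation time creates false correlates.* This would need a factor related to entry date or time observed, and the documents show none.
- *That testing laboratory change against outcomes is biased by a known amount.* A change may follow the event or be missing because of it, but the size and direction are unknown. This point and the follow-up conflict are secondary.

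The consequence for this trial is also limited. Section 12.1 reports that "5 participants were enrolled for multifaceted interventions" and that none completed, so no reported result is affected.

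**Conclusion.** The concern holds in this form. Section 9.4 commits to stepwise logistic regression at p<0.05 with no candidate list, entry rule, event minimum or exploratory label. For fractures it cannot work: 1.2 to 2.8 events are expected in 60 person-years, and 2.5 to 5.6 even if FRAX selection doubled the rate. That conclusion survives every reading of the stage mapping in Section 2.1.

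For commoner outcomes the risk is chance selection, at a frequency that depends on the entry test, the number of candidates and the event risk, all of which are assumed. The multivariable model also does not address the two rates named in Section 9.2.1; the 14 to 37% of falls lost rests on an assumed fall rate and Poisson counts.

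The plan should be changed, chiefly for the sake of any reuse of it.

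**What to change.** In Section 9.4:

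1. Delete stepwise selection.
2. Report deaths, first cardiovascular events and first fractures as counts with person-years and exact Poisson 95% CIs. Report falls as a rate with an interval that allows for repeat falls.
3. Fit no multivariable model for fractures.
4. Model falls only if there are enough fallers (for example about 10 per covariate, a rule of thumb). Use negative binomial or robust Poisson regression with a log person-time offset and one or two pre-specified baseline covariates. Otherwise report falls descriptively.
5. Label every correlate analysis exploratory.
6. Drop tests of laboratory change against outcomes, or limit them to Day 1 to month-3 change against falls after month 3, under the same event minimum.

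Also reconcile the follow-up length across Sections 3, 6.1 and 9.2.1.

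The cost is analysis wording and a little code. There would be no list of independent correlates, and the falls model might not be fitted. At 0.3 to 1.0 falls per person-year (assumed, with Poisson or dispersion-1 counts), 10 fallers are reached with probability 91 to 100% over a full year and 22 to 100% with even entry over 2020. The 20 needed for two covariates are reached with probability 5 to 100% and 0 to 75%. A month-3 landmark loses earlier falls and anyone not followed to month 3, which is 25% of patients if entry is even over 2020 and follow-up ends on 31 December.

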## **10 DATA COLLECTION AND QUALITY ASSURANCE**

### **10.1 Data Collection Forms**

A trained research coordinator and investigators will be responsible for entry of screening, enrollment, and medical records. Data inconsistencies and data abstraction errors will be dealt with initially by telephone or email with the research coordinator.

### **10.2 Data Management**

Data coordination and management will occur within the National Taiwan University Hospital and its Chu-Tung Branch. Data management procedures will ensure accurate and efficient data collection and analysis; confidentiality, on-demand study monitoring reports. All data will be maintained for participant confidentiality and privacy. Access to data resources will be strictly limited to research coordinator and investigators, and the medical records and paper materials of this project are based on the principle of not leaving the hospital. The typed information will only be the research number of the respondent. All data is locked or placed on an encrypted computer, and only authorized personnel have permission to interpret it. The information collected by this project is only for the project team's medical research and academic publication.

## **11 PARTICIPANT RIGHTS AND CONFIDENTIALITY**

### **11.1 Institutional Review Board (IRB) Review**

This protocol and the informed consent script and any subsequent modifications will be reviewed and approved by the Research Ethics committee of National Taiwan University Hospital responsible for oversight of the study.

### **11.2 Participant Confidentiality and Security**

Information about study participants will be kept confidential. Any data, forms, reports, and other records will not leave the Hospital. All paper records will be kept in a locked file cabinet. For the qualitative interviews, at the completion of the coding and analysis the recordings and the link between study ID and identifying information will be destroyed, thus rendering the data anonymous.

## 12 RESULTS

### 12.1 Number of Patients Screened

A total of 249 patients in outpatient clinic of two investigators were screened for osteoporosis risk assessment. If FRAX® screening criteria for Hip fracture risk: men with risk > 6%, women > 7% or major fracture risk: men > 15%, Women > 12.5% were reached. Those with exclusion criteria were excluded. Finally, from January 1, 2020 to December 31, 2020, 5 participants were enrolled for multifaceted interventions. After the intervention, 5 people had laboratory testing, bone density examination and health education during follow-up but no one completed the study. The study was terminated because of funding was only for one year. A total of 133 patients were screened in National Taiwan University Hospital, and a total of 116 patients were screened in Chu-Tung Branch, with an average age of 75.7 years. A total of 138 patients accounted for 55.4% of men. The average weight of men was 66.3kg, the average women were 57.3kg, and the average serum creatinine level 2.0 mg/dL for men and 1.8 mg/dL for women. The estimated glomerular filtration rate (eGFR) was 41.9ml/min/1.73m^2 for men and 38.1ml/min/1.73m^2 for women (Table 1). In the analysis of the reasons for exclusion, the highest was the lower risk of fractures estimated by FRAX® which accounted for 128 (51.4%), followed by failure to perform behavioral interventions (17.7%) and patients' refusal (15.7%).

